7.2 Secondary study parameters/endpoints

For the following secondary endpoint scores from patient and control group will be used:

- Construct validity

For the following secondary endpoints scores from the patient group will be used:

- Reproducibility
- Content validity
- Interpretability

7.3 Analysis

Primary study parameter

Internal consistency is the main study endpoint. This will be calculated with Cronbach's alpha. Values between 0.70 and 0.95 reflect good consistency.

Secondary study parameters

Reproducibility will be determined to assess the ability to reproduce similar answers during the retest period. This will be calculated using Intraclass Correlation Coefficient (ICC), where ICC scores over 0.7 are acceptable. The limits of agreement (LOA), which is calculated by mean change in scores \pm 1.96 SD are determined as well.

Content validity is subjectively determined by examining whether the questionnaire is measuring the quality of life related to spina bifida.

Construct validity is determined by testing the following hypotheses:

- The control group will have higher scores in the QUALAS than patients with spina bifida.

- Patients who score higher in the KIDSCREEN-27 or WHOQOL-BREF/ICIQ will have higher scores in the QUALAS.

8 Ethical considerations

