7. Handling and storage of data / images / sound recordings / photos / film recordings	12
9. Handling and storage of human material.....	13
10. Exchange, sharing or transfer of data and/or human material and/or images.....	13
11. Amendments.....	13
12. End of study report	13
13. Publication	13
15. References	14
16. Attachments.....	14

List of abbreviations and relevant definitions*

CTA	Clinical Trial Agreement
De novo biobank	A new data, human material or imaging collection
DMP	Data Management Plan
DPIA	Data Protection Impact Assessment
DTA	Data Transfer Agreement
ENT	Ear Nose Throat
Exception consent	Form Care for data Template, in Dutch: Formulier uitzondering toestemming
GCP	Good Clinical Practice
GDPR	General Data Protection Regulation in Dutch: Algemene Verordening Gegevensbescherming
IC	Informed Consent
ICC	Intraclass Correlation Coefficient
ICIQ	International Consultation on Incontinence Questionnaire
IFU	Instruction For Use
LOA	Limits of Agreement
MTA	Material Transfer Agreement
NWTC	Non-WMO Review Committee; in Dutch: Niet WMO Toetsingscommissie
QUALAS-A	QUAlity of Life Assessment in Spina bifida in Adults
QUALAS-C	QUAlity of Life Assessment in Spina bifida in Children
QUALAS-T	QUAlity of Life Assessment in Spina bifida in Teenagers
UAVG	Dutch Act on Implementation of the General Data Protection Regulation; in Dutch: Uitvoeringswet Algemene Verordening Gegevensbescherming
WMO	Medical Research Involving Human Subjects Act, in Dutch: Wet Medisch-wetenschappelijk Onderzoek met Mensen
WHOQOL-BREF	World Health Organization Quality of Life instrument

Summary

Rationale

Patients with spina bifida often experience a decreased quality of life compared to patients without spina bifida. The Quality of Life Assessment for Spina Bifida (QUALAS) is a validated questionnaire to assess the quality of life in children, teenagers and adults with spina bifida, accounting for specific factors, such as bladder and bowel dysfunction. This questionnaire enables us to assess the current spina bifida related quality of life and identify if bladder and bowel dysfunction is of influence.

Objective(s)

To validate the Quality of Life Assessment for Spina Bifida in Children, Teenagers and Adults in Dutch.

Study type

A multicenter prospective validation cohort study.

Study population

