Children aged 8 – 17 years and adults who are diagnosed with spina bifida. As a control group children aged 8 – 17 years and adults without spina bifida will be approached at the Ear-Nose-Throat (ENT) and paediatric clinics.

Methods

The main study parameter is the validation of the Dutch version of the questionnaire. Patients with spina bifida are asked to fill out the QUALAS at two time-points. They are also asked to fill out an extra questionnaire at two time-points, in order to validate the QUALAS. Children and adults in the control groups are asked to fill out the two questionnaires only once.

Burden and risks

No (extra) outpatient visit is required. The questions in the questionnaires are similar to the medical history during an outpatient visit. The burden is therefore minimal for these patients. Participation in this study will not influence patient treatment.

Recruitment and consent

Parents of children and children and adults who meet the inclusion criteria and none of the exclusion criteria will be informed orally about this study by their treating urologist during a regular visit. A patient information and consent form will be handed over to the parents and children over eight years of age and adults. Parents of children and children and adults at the ENT clinic will be approached by the local urologist for participation for this study. If they are willing to participate they will be asked to sign informed consent and fill out the questionnaire.

Introduction and rationale

Patients with spina bifida often face challenges in different areas. It is common to have a dedicated team of medical specialists for yearly follow-up [1]. This team includes paediatricians, neurosurgeons, orthopaedics, urologists and rehabilitation specialists. Patients with spina bifida may experience symptoms in each of these areas which will have an impact of these patient's quality of life [2]. From the urologist perspective urinary incontinence and faecal incontinence have a high impact on quality of life [3].

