1. Questionnaires to evaluate quality of life in patients with spina bifida do not incorporate these specific symptoms. The QUAlity of Life Assessment in Spina bifida in Children (QUALAS-C), QUAlity of Life Assessment in Spina bifida in Teenagers (QUALAS-T) and The QUAlity of Life Assessment in Spina bifida in Adults (QUALAS-A) have been developed to take these symptoms into account when assessing quality of life. These questionnaires are validated in the United States [4,5]. For children aged 8-12 years the QUALAS-C version is available. For children between 13-17 years of age the QUALAS-T version is available. For adults the QUALAS-A version is available.

Currently, no versions of the QUALAS-C, QUALAS-T, QUALAS-A questionnaires are available in Dutch.

With the QUALAS-C, QUALAS-T and QUALAS-A we will be able to assess spina bifida related quality of life and monitor the development over time. This will enable clinicians to offer improved standardized care.

Objective(s)

2. The aim of this study is to validate the QUALAS questionnaire for children, teenagers and adults in Dutch.

3. Study type

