5.1. Research methods

This is a multicenter prospective cohort validation study of the QUALAS questionnaire. This is a spina bifida related quality of life questionnaire. We will validate the QUALAS using the validated KIDSCREEN-27 for children 8-17 years of age and the World Health Organization Quality of Life instrument (WHOQOL-BREF) and (International Consultation on Incontinence Questionnaire) ICIQ for adults [7]questionnaires to determine spina bifida related quality of life in a standardized manner.

All patients are subject to treatment at the department of Paediatric Urology in Erasmus MC–Sophia or University Medical Center Groningen. Participation in this study will not interfere with their treatment.

For this study two different phases are distinguished:

- **Phase 1:** The QUALAS will be translated following a standardized translation process [8]. This includes three forward translations by Dutch native speakers, one backward translation by a English native speaker and face-to-face testing in the target population.
- **Phase 2:** Children of 8 years and older and adults are asked to fill out the questionnaires, QUALAS and KIDSCREEN for children 8-17 years of age and the WHOQOL-BREF and ICIQ for adults, and repeat filling out the QUALAS questionnaire one week later. We ask all parents to fill out the questionnaire in order to secure a constant answer during the study. Children of 8 years and older and adults in the control group are asked to fill out the QUALAS and KIDSCREEN-27 for children 8-17 years of age and the WHOQOL-BREF and ICIQ for adults. Internal consistency, criterion validity, construct validity an reproducibility will be determined.

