7.1 Main study parameters/endpoints

Internal consistency is the main study endpoint. Total scores of the patient and control group will be used to determine this endpoint.

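### Construct-validity hypothesis 2 predicts one positive sign for KIDSCREEN-27, WHOQOL-BREF and ICIQ alike; if a higher ICIQ score means more incontinence, the sign is reversed for QUALAS-A with ICIQ

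*Protocol*

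**What the plan says.** Protocol section 7.3 rests construct validity on two hypotheses. The first expects the control group to score higher on the QUALAS than the patients. The second is "Patients who score higher in the KIDSCREEN-27 or WHOQOL-BREF/ICIQ will have higher scores in the QUALAS". It gives no separate direction for the ICIQ and mentions no recoding.

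The comparators are set in section 5.1: KIDSCREEN-27 for ages 8 to 17, and "the WHOQOL-BREF and ICIQ for adults". The list of abbreviations expands ICIQ as "International Consultation on Incontinence Questionnaire" and describes WHOQOL-BREF as a quality-of-life instrument. The reference list (section 15) cites KIDSCREEN-27 as a quality-of-life measure.

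Two background statements bear on direction. The Summary says "Patients with spina bifida often experience a decreased quality of life compared to patients without spina bifida". The Introduction says "From the urologist perspective urinary incontinence and faecal incontinence have a high impact on quality of life".

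The protocol does not say which ICIQ module is used, or which way any of the three comparators is scored.

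**The concern.** A directional hypothesis is useful for construct validity only if the predicted sign is the one a valid instrument would produce. Hypothesis 2 covers three comparators with one positive sign, yet one of them is named for a symptom and not for quality of life. The Introduction treats that symptom as a burden on quality of life. If the ICIQ score rises with incontinence, patients with higher ICIQ scores should have lower QUALAS-A scores, the opposite of what is written.

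The adult version would then be tested against a prediction that it should contradict precisely when it works. Someone would have to explain the contrary result away or change the sign after seeing the data. Changing it then gives up the benefit of having stated the hypothesis in advance.

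**Working it through.** The protocol gives no figure on this point to reproduce. The check is one of sign, followed by a count of reach.

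**Step 1: direction of the QUALAS.** Hypothesis 1 (7.3) expects controls to score higher. The Summary says quality of life is decreased in patients. Together: higher QUALAS = better.

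**Step 2: direction of the comparators (assumptions, because no scoring is stated).**
- KIDSCREEN-27 and WHOQOL-BREF: higher = better. Support: both are named as quality-of-life measures.
- ICIQ, case A: higher = more incontinence. Support: its name, and the Introduction's account of incontinence.
- ICIQ, case B: higher = better, either as scored or after recoding.

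**Step 3: expected sign against stated sign, by version and comparator.**

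| Pair | Stated | Expected, case A | Expected, case B |
|---|---|---|---|
| QUALAS-C, KIDSCREEN-27 | + | + | + |
| QUALAS-T, KIDSCREEN-27 | + | + | + |
| QUALAS-A, WHOQOL-BREF | + | + | + |
| QUALAS-A, ICIQ | + | − | + |

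Reversed signs: 1 of 4 in case A, 0 of 4 in case B.

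**Step 4: reach.**
- Adult comparators: 1 of 2 (ICIQ, not WHOQOL-BREF).
- QUALAS versions: 1 of 3.
- Secondary endpoints in 7.2: 1 of 4 (construct validity; not reproducibility, content validity or interpretability).
- Primary endpoint: 0 of 1, since "Internal consistency is the main study endpoint" and it does not use the ICIQ.

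**Step 5: illustration of case A.** The protocol names no statistic, test level or expected correlation for hypothesis 2, so these inputs are assumptions: 50 adult patients (the minimum in section 4.5, read as applying to the adult group), a true correlation of size 0.3 to 0.6, and a one-sided test at 0.05. By Fisher's z, the standard error is 1/√(50 − 3) = 1/√47 = 0.146.

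- Chance that the observed correlation is positive when the true value is ρ: Φ(atanh(ρ) × √47). At ρ = −0.3: Φ(−0.310 × 6.856) = Φ(−2.12) = 1.7%. At ρ = −0.4: Φ(−0.424 × 6.856) = Φ(−2.90) = 0.2%.
- Chance of confirming the hypothesis when the predicted sign matches the scoring: Φ(atanh(|ρ|) × √47 − 1.645). At 0.3: Φ(2.12 − 1.645) = 68%. At 0.4: 90%. At 0.5: 98%. At 0.6: 99.9%.
- Chance of a significant positive correlation at ρ = −0.3: Φ(−2.12 − 1.645), below 0.0001. It is smaller still for stronger negative correlations.

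These figures show what case A would imply. They give no evidence on whether case A is the true scoring.

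**The case against.** The strongest reply is that the error is assumed, not shown. No section gives the ICIQ's module or scoring, and its name does not fix which way its score runs. Section 5.1 points the other way: it groups the ICIQ with the other two questionnaires as means "to determine spina bifida related quality of life in a standardized manner". On that wording, scoring higher may be shorthand for reporting better quality of life. Orienting scales so that higher is better is also routine work for an SAP, and the questionnaires themselves are on the attachment list (section 16). Finally, the direction of KIDSCREEN-27 and WHOQOL-BREF is not stated either, so the count of 1 or 0 of 4 depends on a second assumption.

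Much of this stands. The reversal is conditional, both assumptions have to be labelled, and the absence of scoring detail from the protocol is not a fault. What does not fall away is the sign itself. The protocol has fixed it for all three instruments. If a higher ICIQ score is worse, an SAP could not simply add the scoring: it would have to recode the ICIQ or depart from the protocol's hypothesis.

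A reader might go further and infer that the protocol definitely has the wrong sign, or that QUALAS-A would fail validation because of it. The documents support neither. The first needs scoring information that they do not contain. The second needs a rule by which one contrary comparator fails the questionnaire, and none is stated. The size of the estimated association is also the same whichever sign is predicted, so a negative ICIQ result would be visible and interpretable.

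**Conclusion.** The point holds in conditional form and is minor. The protocol fixes a single positive direction across instruments that its own descriptions give reason to think may run in opposite directions. If a higher ICIQ score means more incontinence, and higher KIDSCREEN-27 and WHOQOL-BREF scores mean better quality of life, the prediction for QUALAS-A with ICIQ is reversed and a well-functioning adult questionnaire would contradict it. If a higher ICIQ score is better, the hypothesis is correct as written. The effect is confined to one adult comparator within construct validity. Confidence is medium, because the direction of the ICIQ is inferred from its name and the rationale, not from stated scoring.

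**What to change.** Before analysis, replace hypothesis 2 with one signed hypothesis per comparator, tested in patients, with the sign matched to each instrument's scoring:

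- KIDSCREEN-27 with QUALAS-C and QUALAS-T: positive, if higher is better.
- WHOQOL-BREF with QUALAS-A: positive, if higher is better.
- ICIQ with QUALAS-A: negative, if higher means more incontinence. Alternatively, recode the ICIQ so that higher is better, declare the recoding, and keep the positive sign.

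If the ICIQ as used already scores higher for better, one line saying so settles the matter. The cost is splitting one sentence into three. No additional data, participants or questionnaires are needed.

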8.1 Regulation statement

The study will be conducted according to the principles of the Declaration of Helsinki (version, date, see for the most recent version: www.wma.net), Gedragscode Gezondheidsonderzoek 2022 and in accordance with other guidelines, regulations and Acts (if applicable, please specify).

8.2 Informed consent

Will the subjects be asked for informed consent?

Yes

No, consent already given in previous study (*Upload Participant Information Letter and Informed Consent previous study*)

No, this research will be performed under the exception consent (*Upload form Care for data Template, in Dutch: Formulier uitzondering toestemming*)

Other (e.g. partly, indirectly) *Please describe the situation.*

8.3 Recruitment and informed consent procedures

Adults, parents of children and children who meet the inclusion criteria and none of the exclusion criteria will be informed orally about this study by their treating urologist during a regular visit. A patient information and consent form will be handed over to the adults, and parents and children over eight years of age. The two questionnaires are included in this package as well. When adults, parents and children are willing to participate adults or parents and children over twelve years of age are asked to sign the consent form, and sent it in through the post, along with the first questionnaire and voiding diary in the following week. For children of the ages 16 and 17 only the consent form signed by them is necessary. For all the children of the other age groups a signed consent by the parents is necessary.

Adults, or parents of children and children at the ENT and paediatric clinics will be approached by the local urologist for participation for this study. If they are willing to participate they will be asked to sign informed consent and fill out the questionnaire.

9 Handling and storage of data / images / sound recordings / photos / film recordings

9.1 Data / images / sound recordings / photos / film recordings

Data will be handled confidentially. Only the members of the study team will be able to access the clinical records and data resulting from this study. Patients will not be identified by personal information in any publication following this study.

9.2 Privacy protection

The data will be stored in the Castor information system. A key will be used so that individual data cannot be traced back to the individual patient. Only the local investigators at the Erasmus MC will have access to the key. The researcher analyzing the data will not have the key to track the data back to an individual patient.

9.3 Handling and storage of data

The data will be stored in the Castor information system. A key will be used so that the individual data cannot be traced back to the individual participant.

In line with Erasmus MC guidelines, data will be kept 10 years after it is collected.

9.4 Handling and storage of images / sound recordings / photos / film recordings

Not applicable

9.5 Approval of access to data / images / sound recordings / photos / film recordings

This study will be performed at the Erasmus Medical Center and University Medical Center Groningen. The PI's of both centers will have access to the anonymous data.

10 Handling and storage of human material

10.1 Human material

Not applicable

11 Exchange, sharing or transfer of data and/or human material and/or images

The data will be collected and stored within the Erasmus MC in the Castor program. Only anonymous data will be collected and shared with collaborating colleagues from University Medical Center Groningen. A DTA is attached.

12 Amendments

Amendments are changes made to the research after a favorable opinion by the accredited METC has been given. All amendments will be notified to the METC that gave a favorable opinion.

Non-substantial amendments will not be notified to the accredited METC, but will be recorded and filed by the sponsor.

13 End of study report

Within one year after the end of the study a final study report will be submitted with the results of the study, including any publications/abstracts of the study.

14 Publication

Do you have the intention to submit the study results in a manuscript for publication in a journal:

Yes

No, *please motivate*

When the required number of participants has been reached, the results will be analysed and a manuscript will be drawn up for publication. A final study report will be written after submission.

The expected duration of the study is 1 year.

15 References

